12.2 Subject demographics and other baseline characteristics

Demographics and baseline characteristics

Summary statistics will be presented for continuous demographic and BSL characteristic variables for each treatment group and for all subjects in the randomized set. The number and percentage of subjects in each category will be presented for categorical variables for each treatment group and all subjects.

The following demographic variables and BSL disease characteristics will be summarized by treatment groups:

- Gender, age, race, ethnicity, weight, height, and BMI
- Anti-TNF treatment history (naïve or inadequate responder), [REDACTED] and other disease-related measures (e.g. [REDACTED] presence of enthesitis, presence of dactylitis, time since first diagnosis of psoriatic arthritis, PASDAS, subjects with psoriasis $\geq 3\%$), number of prior biologic PsA therapies, dose of MTX or other DMARD at randomization.

Medical history

Any significant prior or active medical condition at the time of signing informed consent will be coded using the MedDRA dictionary. These medical conditions will be summarized by primary system organ class and preferred term.

To establish a baseline level of cardiovascular risk, the number and percentage of subjects with pre-solicited cardiovascular risk factors will be summarized by treatment group. The number of cardiovascular risk factors that each subject has will also be summarized by treatment group. If it is unknown whether or not a subject currently or previously experienced a specific cardiovascular risk factor, it will be assumed that cardiovascular risk factor did not occur for that subject.

12.3 Treatments

Study treatment

The analysis of study treatment data will be based on the safety set. The number of active and placebo administrations received will be presented by treatment group.

The duration of exposure to study treatment will also be summarized by treatment group. In addition, the number and percentage of subjects with cumulative exposure levels (e.g. any exposure, ≥ 1 week, ≥ 2 weeks, ≥ 3 weeks, ≥ 4 weeks, ≥ 8 weeks, etc.) will be presented. **Prior and concomitant medication**

Prior and concomitant medications will be summarized in separate tables by treatment group. Prior medications are defined as treatments taken and stopped prior to first dose of study treatment. Any medication given at least once between the day of first dose of randomized study treatment and the date of the last study visit will be a concomitant medication, including those which were started pre- BSL and continued into the period where study treatment is administered.

Medications will be presented in alphabetical order, by Anatomical Therapeutic Classification (ATC) codes and grouped by anatomical main group. Tables will show the overall number and percentage of subjects receiving at least one treatment of a particular ATC code and at least one treatment in a particular anatomical main group.

Significant prior and concomitant non-drug therapies and procedures will be summarized by primary system organ class and MedDRA preferred term.

The number and percentage of subjects receiving prior and concomitant PsA therapy will be presented by randomized treatment group as well as the reasons for stopping their therapies (primary lack of efficacy, secondary lack of efficacy, lack of tolerability, other).

12.4 Analysis of the primary endpoint(s)

Details of the testing strategy including primary and secondary endpoints are provided in [Section 12.5](#).

12.4.1 Definition of primary endpoint(s)

The primary efficacy variable will be ACR50 response at Week 16. The analysis of the primary efficacy variable will be based on the FAS subjects. Primarily, CRP will be used instead of ESR to calculate ACR response; ESR will only be used in the event CRP is missing.

The primary estimand is defined as follows:

- A. Population: defined through appropriate inclusion/exclusion criteria to reflect the targeted psoriatic arthritis population
- B. Variable: composite of remaining on the study and on randomized treatment through 16 weeks and achieving ACR50 response at 16 weeks
- C. Intercurrent event: the intercurrent event is captured through the variable definition
- D. Population-level summary: Difference in marginal response proportions for comparison between treatments

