6.2.2 Prohibited medication

Use of the treatments displayed in [Table 6-1](#) is NOT allowed after the start of the washout period unless specified otherwise below.

Live vaccines should not be given until 12 weeks after last study treatment administration.

Table 6-1 Prohibited medication

Medication	Washout period (before randomization)	Action (after randomization)
Any biologic drugs, including but not limited to TNF α inhibitors, secukinumab, or other biologic drugs targeting IL-17 or IL-17 receptor 
• Etanercept• Infliximab• Adalimumab, golimumab, certolizumab	Biological immunomodulating agents > 3 different TNF α Inhibitors: never 
• 4 weeks• 8 weeks• 10 weeks	Discontinue investigational treatment
Any cell-depleting therapies including but not limited to anti-CD20 or investigational agents [e.g., alemtuzumab (Campath), anti-CD4, anti-CD5, anti-CD3, and anti-CD19]	Never	Discontinue investigational treatment
Conventional synthetic DMARDs (with the exception of MTX) and ts-DMARDs including apremilast, tofacitinib etc	4 weeks	Discontinue investigational treatment
Leflunomide	8 weeks	Discontinue investigational treatment
Leflunomide with cholestyramine washout	4 weeks	Discontinue investigational treatment

Medication	Washout period (before randomization)	Action (after randomization)
Any investigational treatment or participation in any interventional trial	4 weeks or 5 half-lives (whichever is longer)	Discontinue investigational treatment
Unstable dose of NSAIDs (including selective COX-2 inhibitors)	2 weeks	Discontinue investigational treatment. (Dose adjustments allowed after week 16) Discontinuation of investigational treatment may be required on a case by case basis.
Analgesics other than NSAIDs, paracetamol/acetaminophen, and low strength opioids PRN +	2 weeks	Discontinue investigational treatment
Systemic corticosteroids > 10 mg prednisone equivalent (until Week 16)*	2 weeks	If administered due to a medical urgency unrelated to the patient's arthritis, study treatment should be interrupted until the steroid is discontinued. If not administered for a medical urgency or for use related to the patient's arthritis, then discontinuation of investigational treatment may be required on a case by case basis

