Unstable dose of systemic corticosteroids ≤ 10 mg prednisone equivalent (until Week 16)*	2 weeks	Discontinue investigational treatment (Dose adjustments allowed after week 16) Discontinuation of investigational treatment may be required on a case by case basis.
Intra-articular corticosteroids injections, (until Week 16)*	4 weeks	Discontinue investigational treatment
Intramuscular or intravenous corticosteroid treatment	4 weeks	Discontinuation of investigational treatment may be required on a case by case basis
Live vaccinations	6 weeks	If administered due to a medical urgency, study treatment should be interrupted for 4 months. If administered not for a medical urgency then discontinue investigational treatment
Oral or topical retinoids	4 weeks	Discontinue investigational treatment
Photochemotherapy (e.g. PUVA)	4 weeks	Discontinue investigational treatment

Medication	Washout period (before randomization)	Action (after randomization)
Phototherapy (UVA or UVB)	2 weeks	Discontinue investigational treatment
Topical skin treatments (except in face, eyes, scalp and genital area; only corticosteroids with mild to moderate potency)	2 weeks	Discontinue investigational treatment

* see details about corticosteroid management in [Section 6.2.1](#).

+ Regular dosing with low strength opioids is not permitted.

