12.4.3 Handling of missing values/censoring/discontinuations

Missing data for ACR50 response and other binary efficacy variables (e.g. ACR20, [REDACTED] HAQ-DI[®] response, etc.) for data up to Week 16 will be handled as follows:

- Subjects who drop out of the trial for any reason will be considered non-responders from the time they drop out through Week 16 based on the estimands.
- Subjects who do not have the required data to compute ACR response (i.e. tender and swollen joint counts and at least three of the five ACR core set variables) at BSL and at the specific time point will be classified as non-responders.

Continuous variables (e.g. [REDACTED], [REDACTED], etc.) will be analyzed using a mixed-effects repeated measures model (MMRM) which is valid under the missing at random (MAR) assumption. For analyses of these parameters, if all post-BSL values are missing then these missing values will not be imputed and this subject will be removed from the analysis of the corresponding variable, i.e. it might be that the number of subjects providing data to an analysis is smaller than the number of subjects in the FAS.

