12.4.4 Sensitivity and Supportive analyses

Sensitivity analyses and supportive analyses will be conducted in order to provide evidence that the results seen from the primary analysis are robust. These analyses will center on the deviations in model assumptions, and the treatment of missing data.

Sensitivity analyses

In order to determine the robustness of the logistic regression model used for the primary analysis, ACR50 response at Week 16, further logistic regression models may be conducted which explore the impact of other BSL or disease characteristics on response.

Supportive analyses

The impact of missing data on the analysis results will be assessed as well by repeating the logistic regression model using ways to handle missing data. These may include, but are not limited to:

- Tipping point analysis

Additional supportive analyses will be conducted to examine the effect of TNF α status (naïve or IR) and/or other cDMARDs along with study drug and/or the effect of treatment discontinuation without rescue medication but remaining in the study on the primary endpoint.

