- H₁₁: i.v. secukinumab regimen is not different to placebo regimen with respect to resolution of enthesitis response at Week 16 in the subset of subjects who have enthesitis at BSL.

The graphical approach of (Bretz et al 2009) for sequentially rejective testing procedures is used to illustrate the testing strategy:

Figure 12-1 Hierarchical Testing Strategy

The family-wise error will be set to two-sided $\alpha=5\%$ and it will be controlled with the proposed hierarchical testing strategy.

The hypotheses (H_1) for the primary objective (ACR50 at Week 16) for the i.v. regimen vs. placebo will be tested at α . If H_1 is rejected, then the hypothesis H_2 will be tested at α . If H_2 is rejected, then the hypothesis H_3 will be tested and so on.

Estimand definition for the secondary variables

Estimand definition for the secondary binomial variables is the following:

- A. Population: defined through appropriate inclusion/exclusion criteria to reflect the targeted Psoriatic arthritis population, unless otherwise specified.
- B. Variable: composite of remaining on the study and on randomized treatment through 16 weeks and achieving *variable* response at 16 weeks
- C. Intercurrent event: the intercurrent event is captured through the variable definition
- D. Population-level summary: Difference in marginal response proportions between treatments

The estimand of binary variables is (i.v. secukinumab regimen vs placebo) obtained from a logistic regression model with treatment and randomization stratum (TNF α status –naïve or IR) as factors and weight as a covariate at week 16 in the FAS population. Difference in marginal response proportions will be computed for comparisons of i.v. regimen vs. placebo regimen utilizing the logistic regression model fitted. In the analysis subjects dropping out or being unblinded before week 16 or having missing response data at week 16 are considered as non-responders.

Estimand definition for the secondary continuous variables is the following:

- A. Population: defined through appropriate inclusion/exclusion criteria to reflect the targeted Psoriatic arthritis population
- B. Variable: change from baseline in the *variable* of interest
- C. Intercurrent event: had no intercurrent events occurred before week 16
- D. Population-level summary: difference in variable means between the treatment conditions

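### A patient given high-dose, intramuscular or intravenous steroid for an arthritis flare before Week 16 and kept on study drug is scored on observed response, so a treatment failure can count as a responder

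*Protocol*

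**What the plan says.** **Estimands.** The primary variable (Protocol 12.4.1) is "composite of remaining on the study and on randomized treatment through 16 weeks and achieving ACR50 response at 16 weeks". Attribute C names no event and says only that "the intercurrent event is captured through the variable definition". Section 12.5.1 repeats this composite for the secondary binary endpoints.

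**Non-responder rules.** Section 12.4.3 states: "Subjects who drop out of the trial for any reason will be considered non-responders from the time they drop out through Week 16". It adds patients without the data needed to compute the response. For the secondary binary endpoints, 12.5.1 says that "subjects dropping out or being unblinded before week 16 or having missing response data at week 16 are considered as non-responders". Rescue is not among these conditions.

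**Rescue and steroids.** Section 6.2.3 defines rescue as new or significantly changed therapy for lack of benefit or for worsening. It bars rescue before the Week 16 assessments, but also says necessary rescue will not be withheld, and it makes stopping study drug automatic only for prohibited biologics. In Table 6-1 (section 6.2.2), if systemic steroid above 10 mg is used for the arthritis, "then discontinuation of investigational treatment may be required on a case by case basis". The row "Intramuscular or intravenous corticosteroid treatment" has the same case-by-case wording.

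**Supportive analyses.** The only one in 12.4.4 that mentions rescue looks at "the effect of treatment discontinuation without rescue medication but remaining in the study on the primary endpoint".

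**The concern.** The composite is meant to make failure of the assigned treatment a non-response. It does so for patients who leave the study or stop study drug, and for rescue where Table 6-1 requires stopping. For the two steroid routes above, it does so only if the investigator decides to stop study drug. Two patients with the same flare, the same steroid course and the same Week 16 measurements can therefore be scored differently.

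Systemic steroid can improve every component of the ACR response. The protocol guards against this for intra-articular injections: they require stopping before Week 16, and section 6.2.1.1 has injected joints scored swollen and tender from then on. The systemic, intramuscular and intravenous routes have no matching safeguard in the response scoring.

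At stake are the meaning of the estimated difference and, slightly, its size, for ACR50 (H1) and the other binary endpoints in the hierarchy (H2 to H4, H10, H11).

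**Working it through.** **1. Tracing one patient through the text.** Take a patient with a flare before the Week 16 assessments, given 20 mg prednisone for arthritis (a dose chosen for illustration) and kept on study drug.

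- On study? Yes.
- On randomized treatment? Yes, because Table 6-1 did not require stopping.
- Dropped out, unblinded or missing data? No.
- Result: a responder if ACR50 is met at Week 16.

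The same patient with study drug stopped is a non-responder. The only thing that differs is the stopping decision. Section 12.4.4 does not reach the first patient: its named group stopped treatment and had no rescue, and a tipping point analysis acts on missing data, whereas these data are observed.

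**2. The plan's power figure.** Inputs from Protocol 12.8.1: n = 190 per arm, two-sided 5%, ACR50 8.1% on placebo against 35.9% (150 mg) or 39.6% (300 mg). With pooled variance under the null and p̄ the mean of the two rates,

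power = Φ{ [ |p1 − p0|·√n − 1.96·√(2p̄(1 − p̄)) ] / √(p0(1 − p0) + p1(1 − p1)) }.

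For 8.1% against 35.9%, p̄ = 0.22: (0.278 × 13.784 − 1.96 × 0.5858) / 0.5519 = (3.832 − 1.148) / 0.5519 = 4.86, so power exceeds 99.9%. For 39.6% it is higher. This agrees with the stated figure of approximately 99%.

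**3. Effect of one patient.** 1/190 = 0.53 percentage points in that arm's response rate.

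**4. How many would matter for the test.** Adding k rescued responders to the placebo arm:

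| Comparison | k at which power first falls below 99% | Share of arm | Placebo rate | Power |
|---|---|---|---|---|
| 35.9% (150 mg) | 17 | 17/190 = 8.9% | 17.0% | 0.988 |
| 39.6% (300 mg) | 23 | 23/190 = 12.1% | 20.2% | 0.987 |

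**5. Illustration with assumed rescue shares.** Shift = share rescued and kept on drug × response rate among them. The documents give neither. Assume 1% to 5% of one arm, responding at between 8.1% and 39.6%:

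- lower end: 0.01 × 0.081 = 0.08 points
- upper end: 0.05 × 0.396 = 1.98 points

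| Arm rescued | Difference planned at 27.8 points | Difference planned at 31.5 points |
|---|---|---|
| Placebo only | 27.7 to 25.8 | 31.4 to 29.5 |
| Secukinumab only | 27.9 to 29.8 | 31.6 to 33.5 |

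The lowest power here is 0.99999 (10.08% against 35.9%). A harsher assumption, 10% rescued on placebo and 3% on secukinumab with half responding, gives 27.8 − (0.10 − 0.03) × 0.5 × 100 = 24.3 points and power 0.9999. Equal shares and response in both arms leave the difference unchanged. The planned rates are taken to exclude rescued responders; if they include them, the gap between the two scoring rules is the same size.

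**The case against.** **The protocol does give a rule.** A reader might infer that the estimands leave this patient unscored. They do not: taken literally, the composite scores the patient as observed. Scoring regardless of rescue is a legitimate strategy, and the alternative would fail a patient who had one early intramuscular dose and truly responded later. What stands is that the choice is never stated for this event, it departs from the composite strategy applied to those who stop, and it hangs on a discretionary decision.

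**Conduct rules make the route narrow.** Rescue is barred before Week 16. Section 9.1.1 says the investigator should stop drug for lack of improvement or worsening, and requires stopping for severe or serious adverse events incompatible with study drug, including those needing an unacceptable co-medication. Some flares will be caught this way. This limits the number affected, but for worsening alone 9.1.1 advises stopping and does not require it.

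**The gap might seem to cover all steroid use.** It does not. Intra-articular injection before Week 16 requires stopping. For unstable doses at or below 10 mg, Table 6-1 also says to discontinue, then adds case-by-case wording. On one natural reading the stop is mandatory before Week 16, so that row needs clarifying and is not a second instance of this point.

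**An imbalance would be visible.** Concomitant psoriatic arthritis therapy is tabulated by arm (Protocol 12.3), as are protocol deviations (SAP 2.3.1). This shows an imbalance but does not correct the response rates.

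**The rule may exist elsewhere.** The supplied SAP covers the final database lock and does not repeat the Week 16 analyses. A rule in the Week 16 plan cannot be excluded.

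**Conclusion.** The point holds as a minor one. As the protocol is written, steroid rescue by these routes is scored on observed response when study drug is continued, so a treatment failure under 6.2.3 can be a responder, although attribute C presents the intercurrent event as already captured.

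The firm figure is 0.53 points per affected responder in an arm of 190. The total shift is unknown. The 1.98 points in the illustration is the upper end under assumed inputs, not an expected value. The difference moves toward zero if such rescue is commoner on placebo, which is the likelier case, and is inflated if it is commoner on secukinumab.

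A reader might infer that the primary result, or power for enthesitis and dactylitis resolution, is threatened. The documents do not support that. ACR50 power stays above 99.9% in every case illustrated, and without rescue rates no power loss can be claimed for the other endpoints.

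**What to change.** In both binary estimands (12.4.1 and 12.5.1) and in the non-responder rules (12.4.3 and 12.5.1), count the following as non-response, whether or not study drug is stopped: systemic corticosteroid above 10 mg prednisone equivalent, or intramuscular or intravenous corticosteroid, given as rescue for arthritis before the Week 16 assessments. Derive a flag from the concomitant-medication data (drug, dose, route, date, reason) and set it before unblinding. Report observed response regardless of rescue as a sensitivity analysis.

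Separately, reword the Table 6-1 row on unstable doses at or below 10 mg so that the stop is clearly mandatory before Week 16. Intra-articular steroid needs no change.

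If the Week 16 analysis plan already has this rule, cite it in 12.4.1. SAP 2.11 reports the Week 16 analysis as done, so if that plan lacked the rule, the rescue-as-non-response result can now only be a labelled post hoc check.

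The cost is one clause in the definitions and rules, one flag and one sensitivity analysis. Section 6.2.1.1 already has sites record the drug, the reason and oral steroid dose changes. Response rates may fall slightly, and the flag depends on the reason the site records.

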12.4.2 Statistical model, hypothesis, and method of analysis

The statistical hypothesis for ACR50 being tested is that there is no difference in the proportion of subjects fulfilling the ACR50 criteria at Week 16 in i.v. secukinumab vs. placebo regimen.

Let p_j denote the proportion of ACR50 responders at Week 16 for treatment regimens j , $j=0, 1$ where

- 0 corresponds to placebo regimen,
- 1 corresponds to i.v. regimen,

In statistical terms, $H_0: p_1 = p_0$, $H_{A1}: p_1 \neq p_0$, for the i.v. secukinumab regimen, i.e.

H_1 : The i.v. secukinumab. regimen is not different to placebo regimen with respect to signs and symptoms (ACR50 response) at Week 16

The primary endpoint of ACR50 at Week 16 in the FAS will be evaluated using a logistic regression with treatment and randomization stratum (TNF α status –naïve or IR) as factors and weight as a covariate. Difference in marginal response proportions will be computed for comparisons of i.v. secukinumab vs. placebo regimen utilizing the logistic regression model fitted.

12.4.3 Handling of missing values/censoring/discontinuations

Missing data for ACR50 response and other binary efficacy variables (e.g. ACR20, [REDACTED] HAQ-DI[®] response, etc.) for data up to Week 16 will be handled as follows:

- Subjects who drop out of the trial for any reason will be considered non-responders from the time they drop out through Week 16 based on the estimands.
- Subjects who do not have the required data to compute ACR response (i.e. tender and swollen joint counts and at least three of the five ACR core set variables) at BSL and at the specific time point will be classified as non-responders.

Continuous variables (e.g. [REDACTED], [REDACTED], etc.) will be analyzed using a mixed-effects repeated measures model (MMRM) which is valid under the missing at random (MAR) assumption. For analyses of these parameters, if all post-BSL values are missing then these missing values will not be imputed and this subject will be removed from the analysis of the corresponding variable, i.e. it might be that the number of subjects providing data to an analysis is smaller than the number of subjects in the FAS.

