6.1.3 Treatment arms/group

At baseline, eligible subjects will be randomized to one of the following two treatment arms in a 1:1 ratio (see [Figure 3-1](#)).

Group 1: secukinumab i.v. (6 mg/kg) at BSL, followed by secukinumab 3 mg/kg i.v. every four weeks starting at Week 4 through Week 48 (exposure through week 52).

Group 2: placebo i.v. at BSL, Week 4, 8 and 12 followed by secukinumab 3 mg/kg i.v. every four weeks starting at Week 16 through Week 48 (exposure through week 52).

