8.3 Efficacy

The efficacy outcome measures used in this study are the standard measures used across all PsA trials and required for filing. All efficacy assessments should be performed prior to administration of study treatment.

- American College of Rheumatology (ACR) 20, 50 and 70 responses
- Swollen Joint Count (SJC)/Tender Joint Count (TJC)
- Patient's global assessment of disease activity (VAS)
- Physician's global assessment of disease activity (VAS)
- Patient's assessment of PsA pain intensity (VAS)
- Health Assessment Questionnaire – Disability Index (HAQ-DI $^{\circ}$)
- [REDACTED]
- High sensitivity C-Reactive Protein (hsCRP)
- Erythrocyte Sedimentation Rate (ESR)
- [REDACTED]
- Psoriatic Arthritis Disease Activity Score (PASDAS)
- Patient's global assessment of psoriasis and arthritis disease activity (VAS)
- Minimal disease activity
- Leeds Dactylitis Index (LDI) and dactylitis count
- Leeds Enthesitis Index (LEI)
- [REDACTED]
- Psoriasis Area and Severity Index (PASI)
- [REDACTED]
- Modified Nail Psoriasis Severity Index (mNAPSI)
- Physician global fingernail disease severity assessment (VAS)
- [REDACTED]

Patient reported outcomes (PROs) will be collected using the ediary technology.

The subject should must be given the PRO measure(s) to be completed at the scheduled visit before any clinical assessments are conducted

Details relating to the administration of all PROs are provided in [Appendix 16.12](#).

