Subjects who discontinue study treatment or who decide they do not wish to participate in the study further should NOT be considered withdrawn from the study UNLESS they withdraw their consent (see 'Withdrawal of Informed Consent' section). **Where possible, they should return for the assessments indicated** in the Assessment Schedule. If they fail to return for these assessments for unknown reasons, every effort (e.g. telephone, e-mail, letter) should be made to contact the subject/pre-designated contact as specified in the lost to follow-up section. This contact should preferably be done according to the study visit schedule.

If the subject cannot or is unwilling to attend any visit(s), the site staff should maintain regular telephone contact with the subject, or with a person pre-designated by the subject. This telephone contact should preferably be done according to the study visit schedule.

Subjects who prematurely discontinue or withdraw during a specific treatment period (i.e., Week 16 for treatment period 1 or Week 52 for treatment period 2) should return to site 4 weeks after the last study treatment for the final visit within that treatment period. Subjects should also return for the follow-up visit (Week 60) 12 weeks after the last study treatment (see [Table 8-1](#)). The final visit should be performed before any new treatment is initiated.

The investigator must also contact the IRT to register the subject's discontinuation from study treatment.

If discontinuation occurs because treatment code has been broken, please refer to Emergency breaking of treatment code section. Refer to [Section 6.6.3](#).

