#### Missing data

Missing data for primary and key secondary binary efficacy variables for data up to Week 52 will be handled as follows:

- Subjects who drop out of the trial for any reason will be considered non-responders from the time they drop out through Week 52 for active groups or through Week 16 for placebo group.
- Subjects who do not have the required data at baseline and at the specific time point to compute response will be classified as non-responders.

Data collected after Week 16 will generally be presented as 'observed case'; i.e. all available data for each time point will be included in the analyses. In addition, multiple imputation will be used for ACR50. These will be presented for AIN457 6mg/kg - 3mg/kg treatment group only. Observed data summary will be presented by treatment sequence ([Section 2.2.2](#)).

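### Could a subject who stops randomized treatment before Week 16 but stays in the study still be counted as a responder?

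*Protocol*

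**What the plan says.** The primary variable in Protocol 12.4.1 is a "composite of remaining on the study and on randomized treatment through 16 weeks and achieving ACR50 response at 16 weeks". The same section says that the variable definition is where the intercurrent event is dealt with. Protocol 12.5.1 uses the same construction for the secondary binary endpoints.

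The handling rules come afterwards. On trial drop-out, Protocol 12.4.3 reads "of the trial for any reason will be considered non-responders from the time they drop out through Week 16 based on the estimands"; insufficient ACR data is its only other entry. Protocol 12.5.1 says that "subjects dropping out or being unblinded before week 16 or having missing response data at week 16 are considered as non-responders". SAP 2.5.3 counts trial drop-outs as non-responders "from the time they drop out through Week 52 for active groups or through Week 16 for placebo group", and adds missing data.

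Stopping drug is not leaving the study. Protocol 9.1.1 states: "Subjects who discontinue study treatment or who decide they do not wish to participate in the study further should NOT be considered withdrawn", unless they withdraw consent. It adds: "Where possible, they should return for the assessments indicated".

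For continuous secondaries, Protocol 12.5.1 gives a hypothetical estimand, as if no intercurrent event had happened before Week 16, without saying which events are meant. The estimator is an MMRM under missing at random.

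**The concern.** Read alone, the lists leave a hole. A subject stops infusions early, remains in the study, attends Week 16 and meets ACR50. The estimand calls this a failure, but no listed rule sets it to failure. A programmer working only from Protocol 12.4.3 might keep the subject as a responder. The lists also differ: unblinding appears for the secondary binary endpoints but not in the list covering ACR50.

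For the continuous endpoints, if treatment stop is an intercurrent event, values observed after it do not belong to the hypothetical estimand. The text does not say whether they are used or set to missing, so model and estimand cannot be checked against each other. At stake are the estimates and their meaning, more than the primary test.

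**Working it through.** **Who could be affected.** Both arms are infused at baseline and Weeks 4, 8 and 12 in period 1; the placebo schedule is "placebo i.v. at BSL, Week 4, 8 and 12 followed by secukinumab 3 mg/kg i.v. every four weeks starting at Week 16". Protocol 8.3 adds: "All efficacy assessments should be performed prior to administration of study treatment". The Week 16 assessment therefore precedes the Week 16 infusion. The clear case is a subject who misses one or more of the four infusions through permanent stop, yet has Week 16 data that meet ACR50. Protocol 8 and 9.1.1 bring early stoppers back 4 weeks after the last infusion (a last infusion at Week 8 gives a final visit at Week 12) and ask for scheduled visits only where feasible. Those without Week 16 data are already non-responders.

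**Which rule governs them.** The binary list in 12.4.3 is introduced as covering missing data. Observed off-drug data are not missing, so their absence from the list is expected. The variable in 12.4.1 decides, and it says failure. Protocol 12.4.4 lists stopping treatment while staying in the study as a supportive analysis, which fits a primary analysis that fails such subjects.

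**Unblinding.** Protocol 6.6.3 requires drug to be stopped after emergency unblinding. Under 12.4.1 that subject is no longer on assigned treatment, so the omission from the ACR50 list is mostly closed.

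**The plan's figure.** Inputs from Protocol 12.8.1: n = 190 per arm, 8.1% vs 35.9%, two-sided 5%. Power = Φ[(|p1−p0|√n − 1.96√(2p̄q̄)) / √(p1q1+p0q0)], with p̄ = 0.22. This is Φ[(0.278×13.784 − 1.96×0.5858)/0.5519] = Φ(4.86), above 99.99%. The stated figure of about 99% is met.

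**One subject.** 1/190 = 0.53 points.

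**How many would overturn ACR50.** Planned counts are 0.359×190 ≈ 68 and 0.081×190 ≈ 15 (uncorrected chi-square):
- 41 reclassified, 27/190 vs 15/190: z = 0.0632/0.0322 = 1.963, p = 0.0496.
- 42 reclassified, 26/190 vs 15/190: z = 0.0579/0.0318 = 1.819, p = 0.069.

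**Assumed shares.** The documents give no rate of stopping drug while staying, so I take 2% to 10% per arm. The planned rates serve as the reading that keeps observed data. The shift is f1·q1 − f0·q0, where f is the share off drug and q its response rate.
- 10% in both arms, responding at the planned rates: 0.0359 − 0.0081 = 2.8 points; the difference goes from 27.8 to 25.0.
- 10% active, 2% placebo, same response: 0.0359 − 0.0016 = 3.4 points; 32.3% vs 7.9%, power 99.998%.

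**Continuous example, HAQ-DI** (Table 12-3: difference 0.23, SD 0.507). SE = 0.507×√(2/190) = 0.0520; power = Φ(0.23/0.0520 − 1.96) = 99.3%. If 10% of the active arm returned to the placebo mean and those values were used, the difference would be 0.207 and power Φ(0.207/0.0520 − 1.96) = 97.8%.

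**The case for a change.** The strongest counter-argument is that intent is not a rule. The reference to the estimands in 12.4.3 sits in the drop-out bullet only, 9.1.1 separates stopping drug from leaving the study, and 12.4.3 has discontinuations in its heading. One shared list would remove the doubt for a few sentences of text. Power is also thinner lower down the hierarchy. For enthesitis resolution, the last hypothesis, about 105 per arm reproduces the stated 80% (54.6% vs 35.4%; 80.3%). Failing an equal 2% to 10% in each arm gives 78.8% to 72.6%.

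Some of this stands. The lists do not repeat the on-treatment condition, they treat unblinding differently, and the continuous intercurrent events are unnamed. But the enthesitis loss comes from applying the composite, which the plan already specifies; tidier lists would not avoid it. It also rests on an assumed subset size, on assumed stopping rates and on planning rates that exclude treatment-stop failures. Nor do 12.4.3 or 12.5.1 say that the MMRM uses values after treatment stop; they are silent. Rewriting the condition as receipt of all four infusions would go beyond tidying, because it would alter what the estimand requires.

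**Conclusion.** No change is called for. Followed as written, the binary plan already counts a subject who left randomized treatment before Week 16 as a failure. The lists omit a repetition; they set no competing rule. An analyst who reads 12.4.1 beside 12.4.3 reaches the intended result. For the continuous endpoints the missing names are a real gap in detail, but the documents do not show that the model departs from its estimand.

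The effect is 0.53 points per reclassified subject and at most about 3.4 points on ACR50 when off-drug subjects respond at their arm's planned rate. HAQ-DI power goes from 99.3% to 97.8% at worst. These figures rest on assumed off-drug shares of 2% to 10%. The primary conclusion and the stated primary power are not touched.

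One limit remains. The supplied SAP covers only the final database lock, and SAP 2.11 reports the Week 16 analysis as already performed. The plan behind that analysis may state the rule explicitly; these documents cannot show whether it does, or how many subjects it affected.
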